8.1 Efficacy Assessments

Efficacy will be assessed by evaluating the change from baseline PSA for patients with mCRPC (Section 8.1.1). For all patients, DCR (as measured by complete response [CR], PR and SD; Section 8.1.2) will also be evaluated based on change from baseline imaging using RECIST v1.1 criteria. In mCRPC patients, bone lesions will be evaluated using PCWG-3 criteria (Section 8.1.3). Other assessments to be performed during this study are ECOG scores, pain severity (Section 8.1.4), morphine and analgesic use (Section 8.1.6) and change from baseline Patient Reported Outcomes (PROs) using the questionnaires listed in Section 8.1.5 for all patients enrolled in the study.

Efficacy will also be assessed by looking at the skeletal-related events (SREs) and symptomatic skeletal events (SSEs) (Section 8.1.7), progression-free survival (PFS; Section 8.1.8), overall survival (OS; Section 8.1.9), and overall or objective response rate (ORR; Section 8.1.10).

8.1.1 Prostate-specific Antigen (PSA) Response and Progression (mCRPC only)

Blood for PSA assessment will be collected during Screening, on Day 1 of Cycles 1 to 5, every second cycle thereafter (i.e., Cycles 7, 9, 11 etc.), at the EOT/ED Visit and at the 6-, 9- and 12-month Follow-up Visits for all patients including those who discontinue the study for any reason other than disease progression (Table 1-1 [Parts 1 and 2]). Patients who discontinue the study drug for reasons other than disease progression will continue to have PSA evaluated until disease progression, withdrawal of consent, initiation of new anticancer therapy, the end of the 12-month follow-up period or death, whichever comes first. Patients who discontinue the study

drug due to disease progression do not need to provide PSA samples during the Follow-up Visits. PSA will be used as a blood-based biomarker for tracking and monitoring the response state during the study for mCRPC.

A PSA response will be considered as a PSA value reduction $\ge 30\%$ from baseline at the end of Cycles 3 and 6. A PSA response reduction from baseline at any time point will also be assessed as a secondary objective.

According to PCWG-3, a sequence of rising PSA values should be obtained at a minimum of 1-week intervals with a starting value of 2.0 ng/mL. PSA PFS is the time from first dose administration to PSA progression or death.

8.1.2 Disease Control Rate

Disease control rate is measured by the percentage of patients with a best overall confirmed response of CR or PR at any time plus SD from first dose administration until disease progression or death due to any cause or the start of new anticancer therapy. CR, PR plus SD will be assessed based on RECIST v1.1 (Table 1-1 [Parts 1 and 2]).

8.1.3 Tumor Imaging Assessment

In this study, the preferred assessment of soft tissue lesions is CT or MRI scans using RECIST v1.1 criteria and the preferred assessment method for bone lesions is bone scan using PCWG-3.

Tumor imaging using RECIST v1.1 and PCWG-3 criteria will be performed during within 28 days prior to enrollment, every 8 weeks (\pm 7 days) from the first study dose administration up to Week 26, and every 12 weeks (\pm 7 days) thereafter until disease progression (as defined by RECIST v1.1 and PCWG-3 criteria), withdrawal of consent, initiation of new anticancer therapy or death. Tumor imaging should ideally be performed during the rest period before the start of the next treatment cycle.

- If a patient permanently discontinues the study drug due to disease progression according to RECIST v1.1 criteria, a tumor imaging and disease response assessment is not required.
- If a patient permanently discontinues the study drug due to clinical disease progression, a tumor imaging and disease response assessment does not need to be repeated if completed ≤ 28 days after the last dose of study drug.

For patients who permanently discontinue study drug for any reason other than confirmed disease progression, tumor imaging and disease response assessments will continue to be

performed every 12 weeks (\pm 7 days) for up to 12 months after the last dose of the study drug until disease progression, withdrawal of consent, initiation of new anticancer therapy, the patient is lost to follow-up or death, whichever comes first.

- If a patient meets disease progression during the follow-up period according to RECIST v1.1 criteria, a tumor imaging and disease response assessment is not required.
- If a patient meets clinical disease progression during the follow-up period, a tumor imaging and disease response assessment does not need to be repeated if completed ≤ 28 days after the date of clinical disease progression.

For patients who permanently discontinue the study drug or the follow-up period due to withdrawal of consent, the Investigator is to obtain tumor imaging and conduct a disease assessment at the time of the ED Visit or final Follow-up Visit if the patient agrees. A tumor imaging and disease response assessment does not need to be repeated if completed ≤ 28 days of the date of withdrawal of consent.

The same imaging method should be used for a patient throughout the study and images should be read on site. In Part 2 of the study, images should read on site and also be submitted in digital format to a Central Imaging Provider as detailed in the Investigator Site Operations Manual.

Baseline scans shall be assessed and any lesions which can be measured in accordance with RECIST v1.1 or PCWG-3 (CT or MRI) criteria will be noted as "target lesions". Target measurable lesions may either be at the site of irradiation or non-irradiation and the number of lesions will be capped at 10 lesions (for RECIST v1.1). Patients with identified measurable target lesions will be assessed for overall response using RECIST v1.1 criteria. In addition to RECIST v1.1, all measurable lesions (irradiated and non-irradiated) will be measured and monitored for change (including new lesions). To identify abscopal responses, all lesions will be evaluated.

At a minimum, imaging of the chest, abdomen and pelvis should be performed using consistent imaging modality (CT or MRI). Any other areas of disease involvement should be additionally investigated based on the signs and symptoms of individual patients. During the assessments, subsequent to baseline, any other sites at which new disease is suspected should also be appropriately imaged.

Bone scans will be used for qualitative evaluation of lesions and quantitative evaluation of new and/or resolved lesions. Bone scans will be assessed using PCWG-3 criteria.

The RECIST v1.1 and PCWG-3 guidelines for measurable, non-measurable, target and non-target lesions and the objective tumor response criteria are presented in Section 10.5.

8.1.4 Eastern Cooperative Oncology Group Performance Status Score

Eastern Cooperative Oncology Group Performance Status Score⁵ will be evaluated by the Investigator at Screening, Day 1 of Cycles 1 to 3, every second cycle thereafter (i.e., Cycles 5, 7, 9, 11 etc.) and the EOT/ED Visit (Table 1-1 [Parts 1 and 2]). The assessment should be performed by the same Investigator throughout the study, whenever possible.

Table 8-1Eastern Cooperative Oncology Group Performance Status Score

Grade	ECOG Performance Score
0	Fully active, able to carry on all pre-disease performance without restriction.
1	Restricted in physically strenuous activity but ambulatory and able to carry our work of a light or sedentary nature, e.g., light housework, office work.
2	Ambulatory and capable of all selfcare but unable to carry out any work activities. Up and about more than 50% of waking hours.
3	Capable of only limited selfcare, confined to a bed or chair more than 50% of waking hours.
4	Completely disabled. Cannot carry out any selfcare. Totally confined to a bed or chair.
5	Dead

8.1.5 Clinical Outcome Assessment

A Clinical Outcome Assessment is any assessment that may be influenced by human choices, judgement or motivation and may support either direct or indirect evidence of treatment benefit. Patient reported outcome is one of these types of Clinical Outcome Assessments.

Patient reported outcome, an umbrella term referring to all outcomes and symptoms, are directly reported by the patient. Patient reported outcomes have become a significant endpoint when evaluating effectiveness of treatments in clinical trials.

Questionnaires are to be completed before any other study assessments performed on the day of the visit.

The following PRO instruments will be administered for analysis of the PRO endpoints in this study:

• European Organisation for Research and Treatment of Cancer Quality of Life Questionnaire for Cancer Patients (EORTC-QLQ-C30)

The EORTC-QLQ-C30 is a well-established PRO questionnaire developed to monitor health-related Quality of Life (QoL) outcomes among cancer patients (Section 10.6). The questionnaire assesses important functioning domains (e.g., physical, emotional, social) and common cancer symptoms (e.g., fatigue, pain, nausea, vomiting, appetite loss). The questionnaire will be completed at Screening, on Day 1 of Cycles 3 and 5, followed by every 4 cycles thereafter (e.g., Cycle 9, Cycle 13 etc.), and at the EOT/ED Visit (Table 1-1 [Parts 1 and 2]).

• Brief Pain Inventory – Short Form (BPI-SF)

Worst pain, general pain and pain's interference with daily life will be assessed during the study drug using the BPI-SF (Section 10.7). The questionnaire will be completed at Screening, on Day 1 of Cycles 3 and 5, followed by every 4 cycles thereafter (e.g., Cycle 9, Cycle 13 etc.), and at the EOT/ED Visit (Table 1-1 [Parts 1 and 2]). The BPI-SF comprises a total of 15 items measuring 2 domains: pain severity and pain interference. Items measuring pain severity (including 'worst pain') are rated on an 11-point numeric rating scale ranging from 0=No pain to 10=Pain as bad as you can imagine. All BPI-SF items are measured using a 24-hour recall period.

• Functional Assessment of Cancer Therapy – Prostate (FACT-P)

The FACT-P questionnaire is a relevant, worldwide tool used for assessing the health-related QoL in men with prostate cancer. The FACT-P is a 39-item questionnaire composed of the FACT-General (FACT-G) original subscales (Physical Well-being, Social/Family Well-being, Emotional Well-being and Functional Well-being) and a Prostate Cancer Subscale (Section 10.9). Each item is rated on a 5-point scale ranging from 0 (not at all) to 4 (very much). A higher score indicates a better QoL. The questionnaire will be completed by mCRPC patients only at Screening, on Day 1 of Cycles 3 and 5, followed by every 4 cycles thereafter (e.g., Cycle 9, Cycle 13 etc.), and at the EOT/ED Visit (Table 1-1 [Parts 1 and 2]).

• Patient Experience Questionnaire (PEQ)

The Sponsor has developed a questionnaire to evaluate the patient's experience with the suppository dosage form (Section 10.8).

The PEQ will be completed on Day 2 of Cycle 1, Day 1 of Cycle 3 and at the EOT/ED Visit (Table 1-1 [Parts 1 and 2]).

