- * The procedures detailed at Cycle 5 Day 1 will be performed for all subsequent on-site visits (unless otherwise specified). Patients will continue NOX66 administration in each cycle from Day 1 until Day 7 followed by a 7-day rest period (Days 8 to 14).

It is important that PK sampling occurs as close as possible to the scheduled time. In order to achieve this, other assessments scheduled at the same time may be initiated prior to the timepoint. The order of assessments (as applicable to study visit) that should occur before dosing is: 1) PRO questionnaires, 2) vital signs, 3) ECG, 4) PK sampling, 5) dose administration. Blood sampling for safety laboratory assessments will be done prior to dosing. The order of assessments (as applicable to the study visit) that should occur after dosing is: 1) vital signs, 2) ECG, 3) PK sampling. All other procedures can be completed (as applicable to study visit) after the PK sample has been collected. It is critical that the patients record the time of dose in their Patient Study Drug Administration Diary for the PK assessment and the site record the time of blood sampling.

- ^{a.} End of Treatment Visit (EOT) occurs 7 to 10 days after the last dose of study drug. Assessments completed within 7 days prior to the last dose of study drug do not need to be repeated. If a patient discontinues from the study early (Early Discontinuation [ED]), they will have an ED Visit within 7 to 10 days after the last dose of study drug.
- ^{b.} For patients who permanently discontinue study drug for any reason other than confirmed disease progression, tumor imaging and disease response assessments will continue to be performed every 12 weeks (± 7 days) for up to 12 months after the last dose of the study drug until disease progression, withdrawal of consent, initiation of new anticancer therapy, the patient is lost to follow-up or death, whichever comes first.
 - If a patient meets disease progression during the follow-up period according to RECIST v1.1 criteria, a tumor imaging and disease response assessment is not required.
 - If a patient permanently meets clinical disease progression during the follow-up period, a tumor imaging and disease response assessment does not need to be repeated if completed ≤ 28 days after the date of clinical disease progression.
 - Patients who have met disease progression will be contacted every 3 months for survival follow-up.

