2.3.3 Overall Benefit: Risk Conclusion

Considering the measures taken to minimize risk to patients participating in this study, the potential risks identified in association with NOX66 are justified by the anticipated benefits that may be afforded to patients with mCRPC and other solid tumors.

3 Objectives and Endpoints

Objectives	Endpoints				
Primary Objectives and Endpoints					
Part 1 (Dose Escalation):	The primary objective for Part 1 will be determined based on the count of DLTs.				
To determine the MTD and RP2D of NOX66 in combination with low-dose EBRT in patients with any	• MTD is defined as the dose level at which no more than 1 patient out of 6 experiences a DLT at the end of Cycle 1.				
solid tumor	• RP2D is the highest dose administered at which no more than 1 patient out of 6 experiences a DLT at the end of Cycle 1 and the dosage form, including the dosing frequency, is acceptable to patients.				

Table 3-1Objectives and Endpoints

Objectives	Endpoints
 Part 2 (Dose Expansion): Arm 1: To evaluate the effect of NOX66 on PSA response in patients with mCRPC. Arm 2: To evaluate the effect of NOX66 on DCR in patients with BC and NSCLC. 	 PSA response is defined as the proportion of patients with a reduction in PSA in plasma (ng/mL) of ≥ 30% from baseline at the end of Cycles 3 and 6. DCR is measured by the percentage of patients with a best overall confirmed response of CR or PR and SD.
Secondary	V Objectives and Endpoints
Characterize the safety and tolerability of NOX66	Safety and tolerability of NOX66 as determined by AEs, TEAEs, clinical laboratory evaluations, vital signs, 12-lead ECG and physical examinations.
Evaluate the safety and tolerability of both doses of EBRT	Safety and tolerability of both doses of EBRT as determined by AEs, TEAEs, clinical laboratory evaluations, vital signs, 12-lead ECG and physical examinations.
Evaluate the exposure of idronoxil	Concentration of idronoxil and selected metabolites in plasma and derived PK parameters, including but not limited to: C _{max} , T _{max} , AUC _(0-t) , AUC ₍₀₋₆₎ , AUC ₍₀₋₁₂₎ , AUC _(0-inf) , C _{min} and t ₂ , as data permit.

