4.1 Overall Design

This is a Phase 1b/Phase 2a, open-label, multicenter study to determine the safety, tolerability, RP2D, efficacy, pharmacokinetics (PK) and pharmacodynamic (PD) properties of idronoxil when rectally administered as a suppository (NOX66) to patients with any solid tumor (Part 1) and patients with mCRPC, BC and NSCLC (Part 2) who are eligible for low-dose EBRT for at least one symptomatic or minimally symptomatic lesion (for the prevention of symptoms). The study will be performed in approximately 14 sites in Australia, United States (US) and Europe. The study is divided into 2 parts: Part 1 (dose escalation) and Part 2 (dose expansion). The study design allows an exploration of different doses of NOX66 (800 mg, 1200 mg, 1600 mg and 2400 mg) with safety monitoring to ensure the safety of the patients. A Safety Steering Committee (SSC) will review available safety data after the first cycle (21 days) of each dose cohort of NOX66 in Part 1 to determine the maximum tolerated dose (MTD)/RP2D.

In Cycle 1, NOX66 will be administered for 14 days followed by a 7-day rest period on a 21-day cycle. From Cycle 2 onwards, NOX66 will be administered for 7 days followed by a 7-day rest period on a 14-day cycle. Patients will continue to receive NOX66 on a cyclical basis until

disease progression, unacceptable toxicity, withdrawal of consent, start of a new anticancer therapy, withdrawal of the patient by the Investigator or termination of the study by the Sponsor.

The study population consist of patients with mCRPC, BC, NSCLC or other solid tumors who have failed at least one line of prior treatment and for whom, according to the Investigator, are eligible for low-dose EBRT for at least one symptomatic or minimally symptomatic lesion (for the prevention of symptoms).

The dose levels of EBRT will be either:

- 8 Gray (Gy) as a single fraction, or
- 20/25 Gy as 5 fractions given over 5 to 10 days.

The first EBRT dose fraction must be administered on Day 2 of Cycle 1 and the remaining dose fractions will be given between Day 3 and Day 11. The choice of one of the EBRT dose/fractions stated above will be at the discretion of the Investigator and will be determined by the clinical requirements of the patient. EBRT will be administered according to the institutional protocol.

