schedule mentioned in Table 1-3. In addition to PK samples, patients will be monitored for cardiac effects using 12-lead ECGs (Table 1-2). NOX66 will be self-administered by the patients or administered by their care giver at home on all other dosing days as well as the evening doses of NOX66 on PK days (Cycle 1: Days 2, 6 and 14; Cycles 2 and 3: Day 1). The evening dose of Day 1 of Cycle 1 (in Part 1 only) will be administered at the clinical unit. Patients or care givers should always wear gloves when handling and/or during administration of NOX66. The use of a small amount of water-soluble lubricant is advised before rectal administration. No oil- or wax-based lubricants should be used during rectal administration. Further administration instructions are provided in the "Instructions for Administration of NOX66 Suppositories" document. Patients will also attend the study center for EBRT (8 Gy or 20/25 Gy given as 1 or 5 fractionated doses, respectively) on Days 2 to 11 of Cycle 1 depending on the number of fractions to be administered. From Cycle 2 onwards only NOX66 will be administered for 7 days followed by a 7-day rest period (as indicated above). Patients with mCRPC may also receive ADT as maintenance therapy and patients with BC may receive background hormonal therapy during this study. No other anticancer therapy will be allowed during the study. Patients will have an End of Treatment (EOT) Visit within 7 to 10 days after the last dose of study drug. If a patient discontinues the study early (Early Discontinuation [ED]), the patient will have an ED Visit within 7 to 10 days after the last dose of study drug.

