4.1.1 Part 1 (Dose Escalation)

Approximately 30 patients with any solid tumor who require low-dose EBRT will be enrolled sequentially to the four planned NOX66 dose groups (Dose Cohort 1: 800 mg [3 to 6 patients]; Dose Cohort 2: 1200 mg; Dose Cohort 3: 1600 mg; Dose Cohort 4: 2400 mg [3 to 8 patients in each of Dose Cohorts 2 to 4]; total daily dose administered twice a day [BID]). At least 2 patients enrolled in Dose Cohorts 2 to 4 must have mCRPC.

The proposed dose regimen for Part 1 is given in Table 4-1. No intra-subject dose escalation is allowed.

	Dose Cohort					
	1	2	3	4		
Total daily dose	800 mg	1200 mg	1600 mg	2400 mg		
Dosing regimen	400 mg BID	600 mg BID	800 mg BID	1200 mg BID		
Number of suppositories per day	$2 \times 400 \text{ mg}$	2 × 600 mg	$4 \times 400 \text{ mg}$	4 × 600 mg		

Table 4-1Proposed Doses for NOX66 (Part 1)

BID = twice daily

All patients will be closely monitored for any dose-limiting toxicities (DLTs) up to Day 21 of Cycle 1.

Dose escalation will be based on an adapted "3+3" design, where dose cohorts will be expanded for up to 6 patients (Dose Cohort 1) in the event of DLT or up to 8 patients (Dose Cohorts 2 to 4) to allow for robust estimation of PK parameters after being deemed "safe" based on the traditional "3+3" design.

At each dose level, 3 patients will initially be treated with NOX66.

- If none of the first 3 patients enrolled in Cohort 1 experience a DLT during the first treatment cycle, the dose will be escalated to the next level.
- If none of the first 3 patients experience a DLT during the first treatment cycle of Cohorts 2 to 4, then the dose level will be deemed "safe" and up to 5 additional patients will be enrolled to the current dose level for estimation of PK parameters. At the same time (with the exception of Cohort 4), the next dose level will be initiated and the first 3 patients will be enrolled to the escalated dose.
- If 1/3 patients experience a DLT, an additional 3 patients will be enrolled. If 1/6 patients experience a DLT then this dose level will be deemed "safe" and, for Cohorts 2 to 4, 2 more patients may be enrolled for estimation of PK parameters. At the same time, the next dose level will be initiated and the first 3 patients will be enrolled to the escalated dose.
- If > 1/3 or > 1/6 patients experience a DLT, then dose escalation will be halted, and the previous dose will be declared as the MTD.

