7.1.2.1 Safety Steering Committee

The safety of the patients enrolled in this study will be closely monitored on an ongoing basis by an SSC during dose escalation review meetings. The SSC will review clinical data from the study, including safety, available efficacy and PK data (if available), and will ensure the appropriate selection of doses to be used in the dose escalation and dose expansion phases of the study. All safety data collected up to Cycle 1 Day 21 for each patient will be reviewed.

The SSC will consist of:

- The Sponsor's Study Team Physician or a designee.
- Clinical Research Organization's Medical Monitor, who will chair the committee.
- The Investigators or a designee from every participating site, at least from sites which enroll patients in the respective dose cohort.
- Other Sponsor and Parexel team members.

The SSC charter will define the exact membership and who should be present for recommendations to be made.

For the initiation of a new dose level, the SSC will evaluate the available safety, tolerability and PK data (if available) of NOX66 in combination with EBRT. Once 3 patients have completed their DLT assessment period, the SSC will review and assess all available safety data to make recommendations regarding that dose and/or the next dose/study part. The decisions and decision-making regarding the next dose level will be documented and provided to the Investigators prior to dosing of new patients. The final decision regarding dose escalation or dose de-escalation will be made by the SSC.

The SSC will be responsible for the following:

- Assessment of all available safety, tolerability and exposure data during the study.
- Defining patients who have experienced a DLT per protocol definitions of DLT (see Section 7.1.2.2).
- All recommendations regarding dose escalation or dose de-escalation of NOX66. The SSC may recommend proceeding with dose escalation, expand the current dose level with additional patient enrollment or de-escalate the dose to a lower dose level.
- All recommendations regarding modification of NOX66 dosing schedule, if required. The SSC may recommend adjusting the NOX66 dose, dosing frequency or schedule during either Cycle 1 or subsequent cycles. In this situation, the protocol must be amended.
- All recommendations relating to initiation of Part 2 enrollment.
- Recommendation for cessation of dose escalation.

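### The RP2D must be acceptable to patients in dosage form and frequency, but the only scheduled PEQ before a cohort's own post-Cycle 1 review is on Day 2, after 2 of 28 administrations

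*Combined protocol and SAP*

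**What the plan says.** **The criterion.** The RP2D definition in Section 1.1 and Table 3-1 has two limbs. One is a limit of 1 patient in 6 with a DLT. The other is that "the dosage form, including the dosing frequency, is acceptable to patients".

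**The instrument.** Section 8.1.5 introduces the PEQ: "The Sponsor has developed a questionnaire to evaluate the patient's experience with the suppository dosage form". No other questionnaire in the protocol is described in those terms. The timing, also given in Table 1-1 footnote x, is: "The PEQ will be completed on Day 2 of Cycle 1, Day 1 of Cycle 3 and at the EOT/ED Visit". The notes to Table 1-1 fix the predose order on visit days as "1) PRO questionnaires, 2) vital signs, 3) ECG, 4) PK sampling, 5) dose administration".

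**Dosing.** Section 4.1 states: "In Cycle 1, NOX66 will be administered for 14 days followed by a 7-day rest period on a 21-day cycle". All four cohorts dose twice daily (Table 4-1). The morning doses of Days 1, 2, 6 and 14 are given at the study center. Section 4.1 adds: "The evening dose of Day 1 of Cycle 1 (in Part 1 only) will be administered at the clinical unit". Section 6.4 lists only mornings as site doses.

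**The decision.** Under Section 4.1 the SSC reviews each cohort after its 21-day first cycle to determine the MTD/RP2D. Section 7.1.2.1 says of this review: "All safety data collected up to Cycle 1 Day 21 for each patient will be reviewed". It lets the SSC make recommendations on the current dose, the next dose or the next study part once 3 patients have finished the DLT period. Section 4.1.1 declares 2400 mg the RP2D if no DLT is seen there.

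No section names the PEQ as an SSC input or says what level counts as acceptable.

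**The concern.** The acceptability limb needs evidence from repeated use, but the scheduled questionnaire catches a cohort almost at the start of dosing. The PEQ asks about leakage, about feeling the suppository more than an hour after insertion, and about interference with ordinary activities such as cooking, working or leaving home (Appendix 8). Answers given on Day 2, predose, say little about these over two weeks of twice-daily use at home, or about whether that frequency is tolerable for so long. Cohorts 3 and 4 use two suppositories per administration, so burden could differ there from the lower cohorts.

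The stake is the dose taken into Part 2, where 64 to 70 patients (40 in Arm 1 plus 24 to 30 in Arm 2) receive the RP2D. If the SSC declares the dose under review to be the RP2D soon after that cohort's first cycle, the acceptability limb for that dose rests on first impressions, or on information not designed to measure acceptability.

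**Working it through.** No hypothesis test or sample-size formula is involved. The check is a count of days and administrations.

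**1. Reproduce the plan's own figure.** Cycle 1 lasts 21 days and Cycle 2 lasts 14, so Cycle 3 Day 1 = 21 + 14 + 1 = study Day 36. Then 36/7 = 5.1, which falls in Week 6. Table 1-1 puts Cycle 3 dosing in Week 6, so the calendar agrees.

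**2. Exposure before each PEQ.**
- Cycle 1 administrations: 14 days × 2 = 28.
- Before the Day 2 PEQ: Day 1 morning and evening = 2, and 2/28 = 7.1%.
- In Cohorts 3 and 4, with two suppositories each time: 4 of 56, again 7.1%.
- Before the Cycle 3 Day 1 PEQ: 28 + 7 × 2 = 42.

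**3. Home use in Cycle 1, Part 1.** The two descriptions of the Day 1 evening dose give different counts.

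| | Sections 1.1 and 4.1 (evening dose at the unit) | Section 6.4 (only mornings at the site) |
|---|---|---|
| Site administrations | 5 | 4 |
| Home administrations | 28 − 5 = 23 | 28 − 4 = 24 |
| Home administrations before the Day 2 PEQ | 0 | 1 |

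The sections must be reconciled. On either count, nearly all home use comes after the Day 2 PEQ.

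**4. Position relative to the cohort's own review.** The review follows Day 21. The next scheduled PEQ is 36 − 21 = 15 days later. For a patient still on treatment, Day 2 is therefore the only scheduled PEQ by Day 21.

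**5. Position relative to the next cohort's review.** Section 4.1.1 opens the next dose level only after the SSC clears the first 3 patients, who have by then completed 21 days. When the next cohort's first 3 reach Day 21, the earlier cohort's first 3 are at Day 21 + 21 = 42 or later. Since 42 > 36, those still on treatment have reached their Cycle 3 Day 1 PEQ.

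**6. Six patients before declaring.** If patients 4 to 6 of a cohort start after the enrollment halt and complete Cycle 1 before the RP2D is declared, they finish at about Day 42 on the first 3 patients' clock. The first 3 patients' Day 36 PEQs would then also be due. Section 4.1.1 does not make the 2400 mg declaration wait for this.

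**7. Effect of a predose Day 14 PEQ.** It would follow 13 × 2 = 26 of 28 administrations. Under Sections 1.1 and 4.1, 4 of those 26 are at the site (Day 1 morning and evening, Day 2 morning, Day 6 morning), leaving 22 of 23 home administrations covered. Under Section 6.4 the figure is 26 − 3 = 23 of 24.

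**The case against.** The strongest objection is that a cohort's post-Cycle 1 review mainly decides escalation, whereas the RP2D is chosen across cohorts at the end. Cohorts are sequential, so by step 5 a lower dose chosen because a higher one failed will usually have its own Day 36 PEQs, after 42 administrations that were mostly at home. Cohort 3's Day 36 PEQs also describe two suppositories twice daily, the same count and frequency as Cohort 4, and the 600 mg strength is used in Cohort 2. This stands, and it limits the point. A reader might infer that the RP2D is always picked without knowledge of home use, or that two-suppository dosing would be unknown when the dose is chosen. The documents do not support either.

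A reader might also infer that the SSC may not look past Day 21. The Section 7.1.2.1 sentence concerns safety data. The same section gives the SSC all available safety, tolerability and exposure data during the study, and Section 7.1.2.2 lets it consider toxicities from Cycles 2 to 6. Nothing bars later PEQs.

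Third, other Cycle 1 information exists: diaries, returned-suppository counts, adverse events, and site investigators who sit on the SSC. This is fair, but none of it is described as a measure of acceptability. The SSC charter, which might say more, is not among the documents. A patient who stops early could also complete a PEQ at the ED visit before Day 21, but that covers only those who stop.

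What remains is the cohort under review. Cohort 4 has no later cohort to give its Day 36 PEQs time to arrive.

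**Conclusion.** The point holds in limited form, and its severity is minor. For a cohort's own post-Cycle 1 review, the only scheduled PEQ follows 2 of 28 administrations (7%). The gap matters most for 2400 mg, which can be declared the RP2D on absence of DLTs with no requirement to wait for that cohort's Day 36 PEQs. For a lower RP2D, Day 36 data will usually be available.

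This rests on four assumptions:
- Patients are still on treatment.
- The predose questionnaire order is followed on Day 2.
- The cohort's first 3 patients start close together. If starts were spread over 15 days or more, the first patient could reach Day 36 before the third reaches Day 21.
- The next cohort runs to about its own Day 15 (36 − 21) before the lower dose is chosen. An earlier stop for DLTs could precede the lower cohort's Day 36 PEQs.

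The statement that no home dose precedes the Day 2 PEQ depends on Sections 1.1 and 4.1. Under Section 6.4 there is one.

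**What to change.** Add the PEQ, predose, at the existing Cycle 1 Day 14 site visit. The edits are to the PEQ row and footnote x of Table 1-1, Section 8.1.5, and the completion days named in the Appendix 8 instructions. State in Section 7.1.2.1 that the SSC uses the Day 14 PEQ, plus any later PEQs then available, for the acceptability criterion. Reconcile Sections 1.1 and 4.1 with Section 6.4 on where the Day 1 evening dose is given in Part 1.

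The cost is one questionnaire, which Appendix 8 says takes no more than 5 minutes, at a visit that already takes place. No dose, DLT rule or review date changes.
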